1.6 Research Hypotheses

1.6.1 **Primary Hypothesis**

The primary hypothesis to be tested is that delivery of a single 2 mL SC injection of 300 mg tralokinumab at different flow rates has no significant impact on its PK profile as compared to delivery as 2×1 mL injections.

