1.5 Rationale for Conducting the Study

There is an unmet medical need for new therapies for use in subjects unable to gain asthma control using standard asthma controller medications. In Study MI-CP199, treatment with tralokinumab showed evidence of an increase in FEV_1 compared with placebo and an acceptable safety profile; therefore, further study of tralokinumab as a potential therapeutic asthma-controller therapy is warranted.

A target dose of 300 mg tralokinumab administered as 2×1 mL SC injections has been established. Development of a device to support large volume delivery of tralokinumab (by large volume bolus injector or large volume autoinjector) is planned to enable the target dose to be delivered by a single injection rather than 2 individual injections. For this to be feasible, the pharmacokinetic (PK) profile of 300 mg tralokinumab when delivered via different regimens (ie, 2 injections versus 1 injection) should be equivalent and injections of the larger injection volumes (2 mL) must be tolerable for the subject. However, some evidence suggests that larger injection volumes may be associated with a higher incidence of injection site reactions, particularly increased pain intensity (Jorgensen et al, 1996). This is likely due to associated increased SC tissue pressure, which in turn may be influenced by the injection flow rate. The relationship between these variables (injection volume, injection flow rate, and local injection site tolerability) for tralokinumab is currently unknown.

The aim of the present study is to evaluate the PK and tolerability of 300 mg tralokinumab when administered SC by a single larger volume injection of 2 mL at different flow rates compared to that observed with the current method of administration (2×1 mL injections). The data gathered from this exploratory study is expected to characterize the relationship between injection volume, flow rate, and local injection site tolerability of tralokinumab, and the subsequent effect of changes in injection volume and flow rate on the observed PK for the molecule. This information will be used to optimize the design specifications for the future delivery device and to plan future studies.

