3.2.3 Rationale for Endpoints

Primary Endpoint

The primary endpoint of the study is the PK of tralokinumab. Each subject will receive a single dose of 300 mg tralokinumab by one of 4 administration regimens and 57 days of follow up. Based on prior data, the maximum concentration $_{(Cmax)}$ of tralokinumab usually occurs between 2-9 days with a half-life of approximately 21 days following SC administration. Therefore, the sampling scheme will provide adequate samples for the characterization of $_{Cmax}$ and area under the serum concentration-time curve (AUC) parameters through noncompartmental analysis. The PK parameters associated with a single 2 mL injection of tralokinumab at different flow rates will be compared to those associated with 2×1 mL injections of tralokinumab to determine the feasibility of larger volume delivery and to provide information to aid in the design of the final device.

Secondary Endpoints

Injection site pain will be measured using a 100 mm visual analogue scale (VAS; see Appendix 4). Local injection-site tolerability parameters will also be measured, including injection-site itch and visual assessment of the injection site for reactions such as erythema, rash, etc. As local injection-site reactions are of specific interest, they will be recorded in detail on a dedicated and standardized injection-site questionnaire (Appendix 2) at each time point post-injection. These targeted assessment events will not require reporting as adverse events (AEs) on the AE electronic case report form (eCRF), unless they meet one or more of the following criteria:

- Fulfils the criteria for a serious adverse event (SAE)
- Leads to premature termination of the injection during investigational product administration
- Requires concomitant medication or other medically important intervention
- Has an impact on the general condition of the subject as judged by the investigator

These data will be used to determine the overall tolerability of a single 2 mL injection of tralokinumab at different flow rates to determine the feasibility of this approach compared to 2×1 mL injections and to provide information to aid in the design of the final delivery device.

The degree of fluid leakage from the injection site will be assessed immediately following all injections to determine if the flow rates affect delivery of the 2 mL injection volume.

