4.8.2 Sample Size and Power Calculations

The number of subjects planned for this study is based on the number required to obtain adequate PK data while exposing as few healthy volunteer subjects as possible to tralokinumab and procedures. A total of 15 subjects per treatment arm is considered sufficient to detect an approximately 1.5-fold difference in PK parameters between cohorts and will provide exploratory information regarding local tolerability.

A previous single-dose study investigating the PK of tralokinumab (Study CD-RI-CAT-354-1054) showed a coefficient of variation (CV) of 37% for area under the serum concentration-time curve from zero to infinity (AUCO-). Assuming the same CV across the cohorts and using a two-sided two-sample t-test at a significance level of 0.05, with 15 subjects per cohort the study will be 84% powered to detect a 1.5-fold difference in AUC_{0-} between Cohort 1 and any of the other treatment cohorts.

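### The single 2 mL injection is meant to have equivalent PK, but the primary hypothesis is worded as no significant difference and the study is sized on a difference test with no similarity criterion

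*Protocol*

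**What the plan says.** - **Aim.** Section 1.5 says that, for the device to be feasible, the PK profile "when delivered via different regimens (ie, 2 injections versus 1 injection) should be equivalent". Section 3.2.3 says the PK parameters of the 2 mL injections will be compared with those of the two 1 mL injections "to determine the feasibility of larger volume delivery and to provide information to aid in the design of the final device".
- **Hypothesis.** The synopsis and section 1.6.1 state, as the primary hypothesis to be tested, that a single 2 mL injection "at different flow rates has no significant impact on its PK profile as compared to delivery as" two 1 mL injections. Section 1.5 repeats this with slightly different words.
- **Sizing.** Section 4.8.2 takes a CV of 37% for AUC from zero to infinity from an earlier single-dose study. It states that, "using a two-sided two-sample t-test at a significance level of 0.05, with 15 subjects per cohort the study will be 84% powered". The target is a 1.5-fold difference in AUC between Cohort 1 and any other cohort.
- **Analysis.** Section 4.8.3 lists noncompartmental parameters and descriptive statistics for concentrations. It names no test or interval. Section 4.8.1 leaves the details of endpoint analyses to the SAP.
- **Absent from the protocol.** No similarity margin, ratio limit or confidence interval criterion is given.

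**The concern.** Two different questions are in play. Equivalence asks whether the data rule out a difference larger than some stated size. A difference test asks whether the data rule out no difference at all. The primary hypothesis puts the hoped-for conclusion in the place of the null, and failing to reject a null does not confirm it.

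If the outcome were judged by non-significance, the incentive would also run the wrong way: more variability or fewer evaluable subjects would make the hoped-for answer easier to reach. Section 4.1.6 does not replace subjects lost after Day 8, while PK sampling runs to Day 57, so some loss of evaluable subjects is possible.

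At stake is whether this study can be cited, when the delivery device is designed, as having shown that PK is unchanged.

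**Working it through.** **Inputs (protocol section 4.8.2).** CV 37%; 15 per cohort; two-sided alpha 0.05; 1.5-fold difference; two-sample t-test, df = 15 + 15 − 2 = 28.

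**Step 1: the scale.** Assume AUC is log-normal.
- Log-scale SD = √ln(1 + 0.37²) = 0.358.
- Standard error of the difference between two cohort log means = 0.358 × √(2/15) = 0.131.

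**Step 2: reproduce the 84%.**
- ln(1.5) = 0.405; noncentrality = 0.405 / 0.131 = 3.10.
- Noncentral t power, df 28: 84.9%. Taking the log SD as 0.37 directly gives 82.6%.
- The stated 84% lies between these. The arithmetic is sound.

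**Step 3: which observed ratios are non-significant?**
- exp(± t₀.₉₇₅,₂₈ × 0.131) = exp(± 2.048 × 0.131) = 0.765 to 1.307.
- Any observed geometric mean ratio from about 0.76 to 1.31 gives p > 0.05, if the observed SD matches the planning value.

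**Step 4: how often is a true difference non-significant?** One comparison with Cohort 1, 15 per cohort:

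| True AUC ratio | Log SD 0.358 | Log SD 0.37 |
|---|---|---|
| 1.20 | 73% | 74% |
| 1.25 (or 0.80) | 62% | 64% |
| 1.30 | 51% | 53% |
| 1.35 | 40% | 43% |
| 1.50 | 15% | 17% |

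With 12 evaluable per cohort (an assumed loss) and log SD 0.358, the figure rises from 62% to 69% at a ratio of 1.25, and from 15% to 25% at 1.50.

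**Step 5: what do 15 per cohort give for the similarity question?**
- 90% confidence interval: ratio × exp(± 1.701 × 0.131), that is × 0.80 to × 1.25.
- The protocol states no limits, so those below are assumptions. The probability that the whole interval falls inside them (two one-sided tests at 5%, averaged over the sampling of the SD) at log SD 0.358 is:

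| Assumed limits | True ratio 1.00, n = 15 | n per cohort for 80% |
|---|---|---|
| 0.80–1.25 | 8% | 45 |
| 0.70–1.43 | 69% | 18 |
| 0.67–1.50 | 83% | 15 |

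**Step 6: is 0.67–1.50 a safe default?** Under those limits and with 15 per cohort, a true ratio of 1.25 would be declared similar about 39% of the time, and 1.20 about 50%. That 15 per cohort can reach these limits does not show that they are tight enough.

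**The case against.** The best reply has four parts.

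**No decision rule is written.** A reader might infer that the protocol will treat p > 0.05 as proof of equivalence. It does not say so. The t-test appears only in the power statement, and section 4.8.3 is descriptive. This stands, so the point concerns the stated hypothesis and sizing basis, not a written rule.

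**The SAP may cover it.** Section 4.8.1 defers endpoint details, and geometric mean ratios with intervals are common SAP content. Their absence from section 4.8.3 is therefore no fault. But the primary hypothesis and the sample size basis are not deferred; both are set out in this protocol. An SAP written for equivalence would depart from section 1.6.1 and have no matching basis in section 4.8.2.

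**The study is exploratory.** Section 1.5 says so, and the primary objective in section 2.1.1 is to evaluate the PK profile, which reads as estimation. Sizing an exploratory study to detect a large difference is legitimate. This lowers the stakes. It is also a reason not to call the statement a hypothesis to be tested. The synopsis remark about mainly descriptive statistics covers the secondary and exploratory endpoints, not the primary one.

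**A relevant change would not usually be missed.** A reader might infer that clinically important changes would mostly pass as non-significant. The protocol defines no important change, and the one difference it names, 1.5-fold, would be missed only about 15% of the time. Non-significance is the more likely result only up to a true ratio of about 1.30. This objection stands in full.

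**Conclusion.** The mismatch is real and lies in the protocol's own text: an equivalence aim in section 1.5, a no-significant-difference hypothesis in the synopsis and sections 1.5 and 1.6.1, and a difference test as the sizing basis in section 4.8.2. The 84% is right for the question it answers, but that is not the question section 1.5 asks. No p > 0.05 rule is stated, though it is the natural reading of the hypothesis.

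The sizes rest on the protocol's CV, log-normal AUC, 15 evaluable per cohort and unadjusted single comparisons. The ratio of 1.25 and all three sets of limits are illustrations, not figures from the protocol.

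This should be fixed, but it does not invalidate the study. The data will support estimates of the ratios. At 15 per cohort they are very unlikely to support a claim within limits as tight as 0.80–1.25.

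**What to change.** 1. **Synopsis and sections 1.5 and 1.6.1.** Replace the hypothesis with an estimation aim, labelled exploratory: for each of Cohorts 2, 3 and 4 against Cohort 1, estimate the geometric mean ratios of AUC and Cmax on the log scale with 90% confidence intervals.
2. **Same places.** State that a non-significant difference will not be read as equivalence. Any claim of similarity requires the interval to lie wholly inside a margin that the sponsor justifies before data are seen; otherwise the result is inconclusive.
3. **Section 4.8.2.** Keep the 84% statement. Add that 15 per cohort gives a 90% interval of about × 0.80 to × 1.25 around the ratio. Add the probabilities of falling inside assumed limits at a true ratio of 1: about 8% for 0.80–1.25, 69% for 0.70–1.43 and 83% for 0.67–1.50.
4. **Margin.** Do not adopt 0.67–1.50 merely because the sample size can support it; see step 6 of the working.

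**Cost.** Wording in the protocol, carried into the SAP; no extra subjects, visits or samples. The stated claim becomes weaker, and inconclusive becomes a possible result.

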1.6.2 Secondary Hypotheses

The secondary hypotheses to be tested are:

- 1. Increasing the volume of injection of tralokinumab from 1 mL to 2 mL reduces the tolerability of the injection at a given flow rate (as measured by pain, pruritus, and local injection site reactions)
- 2. Decreasing the flow rate of injection of tralokinumab improves the tolerability of the injection (as measured by pain, pruritus, and local injection site reactions)

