3.1.2 Treatment Regimen

A total of 60 subjects will be randomized in a 1:1:1:1 ratio to 1 of 4 cohorts to receive a single SC dose of tralokinumab as described in Table 3.1.2-1. Randomization will be stratified by gender. At a minimum, 5 males and 5 females will be randomized to each cohort; the additional subjects may be of either sex.

Table 3.1.2-1 Investigational Product Dose and Treatment Regimen

Cohort	Ν	Day 1	
1	15	300 mg tralokinumab as 2×1 mL SC injections, with each injection administered at a flow rate of 6 mL/min	
2	15	300 mg tralokinumab as a 1×2 mL SC injection administered at a flow rate of 12 mL/min	
3	15	300 mg tralokinumab as a 1×2 mL SC injection administered at a flow rate of 2 mL/min	
4	15	300 mg tralokinumab as a 1×2 mL SC injection administered at a flow rate of 0.167 mL/min	

N = number of subjects; SC = subcutaneous.

All injections will be administered into the abdomen via the SC route at the flow rates specified above using a syringe pump and SC insertion set.

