4 MATERIALS AND METHODS

4.1 Subjects

4.1.1 Number of Subjects

A total of 60 subjects will be randomized in a 1:1:1:1 ratio to 1 of 4 cohorts to receive a single SC dose of 300 mg tralokinumab administered as either 2×1 mL SC injections at a flow rate of 6 mL/min for each injection (Cohort 1) or a 1×2 mL SC injection at flow rates of 12, 2, or 0.167 mL/min (Cohorts 2, 3, or 4, respectively). At minimum, 5 males and 5 females will be randomized to each cohort; the additional subjects may be of either sex.

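### Secondary Hypothesis 1 compares 1 mL with 2 mL at a fixed flow rate, but no two cohorts that differ in injection volume share a flow rate

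*Protocol*

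**What the plan says.** Protocol section 1.6.2 opens with "The secondary hypotheses to be tested are", and the first of them reads "Increasing the volume of injection of tralokinumab from 1 mL to 2 mL reduces the tolerability of the injection at a given flow rate". The synopsis repeats it. Tolerability means pain, pruritus and local injection-site reactions.

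The cohorts are described the same way wherever they appear (synopsis, 3.1.1, 3.1.2, 4.1.1, 4.5.1.5, 4.6.1). Section 4.1.1 gives the 2 × 1 mL arm "at a flow rate of 6 mL/min for each injection (Cohort 1") and the other three arms a 1 × 2 mL "SC injection at flow rates of 12, 2, or 0.167 mL/min (Cohorts 2, 3, or 4, respectively"). Table 3.1.2-1 likewise ties the lower rate to the single injection: "with each injection administered at a flow rate of 6 mL/min".

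Section 1.5 says that the data gathered "is expected to characterize the relationship between injection volume, flow rate, and local injection site tolerability of tralokinumab", and that the information will feed the specification of the delivery device.

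**The concern.** A hypothesis about volume with the rate held fixed needs at least one flow rate at which both volumes are given. None is. Every comparison of a 1 mL with a 2 mL injection also changes the rate, and the protocol's own second hypothesis says that rate matters for tolerability.

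This is not detail left to a statistical analysis plan. An analysis plan can choose a model, but it cannot supply a comparison that was not randomized. At stake is a statement about volume that would inform the device: its answer could depend on which pair of cohorts is compared, and it would not be an answer to the question as worded.

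**Working it through.** **Inputs.** Volumes and rates come from Table 3.1.2-1, insertion sets from section 4.5.1.5, and scoring rules from sections 4.3.3.2 to 4.3.3.4.

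**Step 1: duration per injection = volume / rate.** The protocol's own figure is 12 minutes for Cohort 4 (section 4.3.3.2). 2 / 0.167 = 11.98 min, so it reproduces. The full set:

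| Cohort | Volume per injection | Rate (mL/min) | Duration per injection | Insertion set |
|---|---|---|---|---|
| 1 | 1 mL (two sites) | 6 | 1/6 min = 10 s | winged needle, 45° |
| 2 | 2 mL | 12 | 2/12 min = 10 s | winged needle, 45° |
| 3 | 2 mL | 2 | 2/2 min = 60 s | soft cannula, 90° |
| 4 | 2 mL | 0.167 | 11.98 min, about 719 s | soft cannula, 90° |

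**Step 2: look for a pair with different volume and equal rate.** Four cohorts give 6 pairs.

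| Pair | Volume differs | Rate ratio (second / first) | Same set |
|---|---|---|---|
| 1 v 2 | yes | 12/6 = 2.0 | yes |
| 1 v 3 | yes | 2/6 = 0.33 | no |
| 1 v 4 | yes | 0.167/6 = 0.028 | no |
| 2 v 3 | no | 2/12 = 0.17 | no |
| 2 v 4 | no | 0.167/12 = 0.014 | no |
| 3 v 4 | no | 0.167/2 = 0.084 | yes |

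Three pairs differ in volume, and none of them has a rate ratio of 1. Cohorts 1 and 2 match on duration per injection and on insertion set, not on flow rate.

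**Step 3: what each volume contrast estimates.** As an illustration, let V be the effect of volume, b the effect per unit of log rate, and S the effect of changing the insertion set and angle. Leave aside the number of punctures.

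- Cohort 2 − Cohort 1 = V + b ln(2.0) = V + 0.69b
- Cohort 3 − Cohort 1 = V + b ln(0.333) + S = V − 1.10b + S
- Cohort 4 − Cohort 1 = V + b ln(0.0278) + S = V − 3.58b + S

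None equals V unless b is zero (and S too, in the last two). If faster is worse (b > 0, as Hypothesis 2 holds), the first contrast leans towards Hypothesis 1. The rate term in the other two leans against it, but S has unknown sign, so their net direction cannot be stated.

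**Step 4: what Cohort 1 measures.** Pain and pruritus are scored once for both sites combined; for local reactions the more severe site is recorded. Cohort 1 therefore gives the tolerability of two 1 mL injections with two punctures, not of one 1 mL injection. The comparison available with Cohort 2 is 2 × 1 mL versus 1 × 2 mL.

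**Power figure.** Section 4.8.2 states 84% power for a 1.5-fold difference in AUC from zero to infinity. With CV 37%, the log-scale SD is √ln(1 + 0.37²) = 0.358; a two-sided t-test at 0.05 with 15 per cohort (28 df) and difference ln(1.5) = 0.405 gives 84.9%. The figure reproduces. It concerns pharmacokinetics only; the protocol states no power for the secondary hypotheses.

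**The case against.** **A model could separate the two factors.** A reader might infer that volume and rate are completely aliased and that the hypothesis cannot be tested at all. That goes too far. Rate takes three values within the 2 mL volume, and 6 mL/min lies between 2 and 12, so an additive model in volume and log rate is estimable. Also, if slower delivery is never worse, poorer tolerability in Cohort 3 or 4 than in Cohort 1 would point to something other than rate. This part of the objection stands, and it limits the point to the absence of a direct contrast. It does not rescue the hypothesis. The protocol names no such model, and between Cohorts 2 and 3 the rate and the insertion set change together. Adding a term for the set gives four parameters for four cohort means, with nothing left to check the model, and a rate slope that rests on Cohorts 3 and 4 alone and must be extrapolated upwards.

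**Concurrent injections.** Section 4.5.1.5 describes the two Cohort 1 injections as concurrent. If they ran simultaneously, total delivery would be 2 × 6 = 12 mL/min, equal to Cohort 2. But the rate is stated per injection, and references to a first and a second injection (4.3.3.2, 4.5.1.5) suggest sequential delivery. If the rate is summed over sites, the volume must be summed too, and then it does not differ between Cohorts 1 and 2.

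**The study is exploratory.** The primary endpoint is pharmacokinetic, no objective asks for a volume effect at fixed rate, and the tolerability data are summarised and explored (4.8.4.2 to 4.8.4.4). The feasibility question, one 2 mL injection against two of 1 mL, is served directly by the cohorts. This stands and lowers the severity. It does not make a stated hypothesis match a comparison the design lacks.

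**Conclusion.** Hypothesis 1 is wrong as written. Of three volume contrasts, none holds the flow rate constant, and the rate ratios to Cohort 1 are 2.0, 0.33 and 0.028. This rests only on the cohort definitions, which are consistent throughout, and on reading the rate per injection, as the protocol states it.

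A reader might go on to infer that any conclusion on volume will be wrong, or that the trial is compromised. The documents do not support either. An error would need a rate effect to exist and a volume-only conclusion to be drawn. The primary objective and its power are untouched, and Cohort 1 versus Cohort 2 remains a useful comparison. The point is a mismatch between a secondary hypothesis and the design in an exploratory part of the study, below must-fix.

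**What to change.** - In the synopsis and section 1.6.2, restate Hypothesis 1 as the contrast the design contains: 2 × 1 mL versus 1 × 2 mL, Cohort 1 versus Cohort 2, at equal duration per injection (10 s) and with the same insertion set.
- State beside it that volume per site, flow rate and number of punctures change together in that contrast, and that Cohort 1 is scored as one combined, or most severe, assessment of two sites. Note also that the assessor cannot be blinded for Cohort 1 (4.6.1, 4.6.2).
- In section 1.5, qualify rather than delete the sentence on characterising the relationship, so that it does not claim a volume effect separate from flow rate. The three 2 mL cohorts still inform on rate, subject to the change of insertion set between Cohort 2 and Cohorts 3 and 4.
- If the sponsor wants the hypothesis as it stands, the hypothesis and the cohort definitions must be reconciled before dosing. How to do so is the sponsor's decision.

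The rewording adds no subjects or procedures. Its cost is a narrower stated conclusion.
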